8.4 Data Monitoring Committee

Not required.

8.5 Adjudication Committee

Not required.

9 Data analysis

A designated Contract Research Organization will perform the statistical analysis.

It is planned that the data from all centers that participate in this protocol will be combined, so that an adequate number of patients will be available for analysis.

Unless otherwise specified, all statistical tests will be conducted against a two-sided alternative hypothesis, employing a significance level of 0.05.

Efficacy, safety, and other data will be summarized. For continuous variables, summary statistics (mean, standard deviation, median, 25th and 75th percentiles, interquartile range, minimum, and maximum) at each time point and for change from baseline to each time point will be reported by treatment group.

9.1 Analysis sets

The following analysis sets will be used for the statistical reporting and analyses:

Randomized Set: The Randomized Set includes all randomized patients.

Safety Set: The Safety Set includes all patients who received at least one dose of study medication. Patients will be included in the analysis according to treatment received.

Full Analysis Set: The Full Analysis Set comprises all patients to whom study medication has been assigned. Patients inappropriately randomized (e.g., IRT was called in error for randomization of a screen failed subject) will be excluded from this analysis set. Following the intent-to-treat principle, patients will be analyzed according to the treatment they were assigned to at randomization.

9.2 Patient demographics and other baseline characteristics

Data will be summarized with respect to demographic and baseline characteristics of all patients, the subgroup of patients with dactylitis at baseline, and the subgroup of patients with enthesitis at baseline, for the Randomized Set and the Full Analysis Set.

9.3 Treatments

The number of patients and the length of time (in days) exposed to each treatment will be summarized for the Safety Set.

Concomitant medications will be summarized by treatment using frequency counts and percentages for the Safety Set.

Any condition entered as medical history or current medical condition at baseline will be coded using the MedDRA dictionary for the Safety Set. They will be summarized by system organ class and preferred term of the MedDRA dictionary.

9.4 Analysis of the primary variable

9.4.1 Variable

The primary efficacy variable is ACR20 response (yes, no). The primary analysis time point will be at Week 16.

9.4.2 Statistical model, hypothesis, and method of analysis

Let π_j denote the probability of an ACR20 response at Week 16 for treatment group j , $j = 0, 1, 2$, where 0 corresponds to placebo, 1 corresponds to secukinumab 150 mg, and 2 corresponds to secukinumab 300 mg. Accordingly, $\pi_j/(1 - \pi_j)$ is the odds for treatment group j , $j = 0, 1, 2$.

The following null hypotheses (H_{01} and H_{02}) will be tested against their corresponding alternative hypotheses (H_{A1} and H_{A2}):

$$H_{01}: [\pi_1/(1 - \pi_1)]/[\pi_0/(1 - \pi_0)] \leq 1 \text{ versus } H_{A1}: [\pi_1/(1 - \pi_1)]/[\pi_0/(1 - \pi_0)] > 1$$

$$H_{02}: [\pi_2/(1 - \pi_2)]/[\pi_0/(1 - \pi_0)] \leq 1 \text{ versus } H_{A2}: [\pi_2/(1 - \pi_2)]/[\pi_0/(1 - \pi_0)] > 1$$

The primary efficacy variable will be analyzed at each time point using a logistic regression model with treatment (3 treatment groups), methotrexate usage at baseline (yes, no), and body weight as explanatory variables (Stokes, Davis, and Koch, 2012). The odds ratios for each dose of secukinumab versus placebo, 95% confidence intervals for the odds ratios, and p-values based on the fitted model will be reported. If the p-value for a dose of secukinumab versus placebo is < 0.05 and the corresponding odds ratio is greater than 1, statistical significance in favor of that dose of secukinumab is shown.

The primary analysis of the primary efficacy variable will be based on the Full Analysis Set.

9.4.3 Handling of missing values/censoring/discontinuations

Patients who discontinued prematurely for any reason will be considered non-responders from the time they discontinued. Patients who do not have the required data to compute ACR response (i.e., tender and swollen joint counts and at least three of the five ACR domains) at baseline and at the specific time point will be classified as non-responders.

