 - Patients who did not meet the responder criteria at Week 16, 28 or 40 will start receiving secukinumab 300 mg s.c. every 4 weeks and will continue this dose up to Week 48.
- Patients on placebo (**Group 3**) regardless of their responder status will start receiving secukinumab 300 mg s.c. every 4 weeks from Week 16 up to Week 48.

Rescue medication will not be allowed during the day of the clinical visit and before completion of Week 16 assessments ([Section 5.5.6](#)). Although no subject will be restricted from receiving necessary rescue medications for lack of benefit or worsening of disease, patients will be discontinued from the study if rescued with prohibited biologics (as described in [Section 5.5.8](#)) and should obtain end of study assessments at the earliest possible date, provided consent to do so has not been withdrawn.

Figure 3-1 Study design

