5.5.6 Rescue medication

Rescue medication is defined as any new therapeutic intervention or a significant change to ongoing therapy made because a subject is experiencing either no benefit from participation in the trial or worsening / exacerbation of their disease.

Rescue medication must not be used before completion of Week 16 assessments.

Changes in NSAIDs concomitant therapy is permitted after Week 16 assessments per investigator's clinical judgment. Any use of rescue medication must be recorded on the corresponding Concomitant Medications eCRF.

Please see [Section 5.5.7](#) for additional details.

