5.5.9 Discontinuation of study treatment

Study treatment must be discontinued if the investigator determines that continuation of study treatment would result in a significant safety risk for a subject. The following circumstances **require** study treatment discontinuation:

- Withdrawal of informed consent
- Emergence of the following adverse events:
 - a. Any severe or serious adverse event that is not compatible with administration of study medication, including adverse events that require treatment with an unacceptable co-medication
 - b. Onset of lymphoproliferative disease or any malignancy except for treated basal cell carcinoma, treated actinic keratoses, treated in situ carcinoma of the cervix or non-invasive malignant colon polyps which are being or have been removed
 - c. Life-threatening infection
- Any laboratory abnormalities that in the judgment of the investigator are clinically significant and are deemed to place the subject at a safety risk for continuation in the study (A general guidance on clinically notable laboratory values is provided in ([Appendix 1](#))).
- Pregnancy
- Use of any biologic immunomodulating agent except secukinumab (please refer to [section 5.5.8](#) for the other prohibited medications). Any protocol deviation that results in a significant risk to the subject's safety

In addition to these requirements for study treatment discontinuation, the investigator should discontinue study treatment for a given subject if there is a lack of improvement or worsening of their symptoms, or if on balance, he/she thinks that continuation would be detrimental to the subject's well-being.

For any subject whose treatment code has been broken inadvertently for any reason, the appropriate personnel from the site and Novartis will assess whether study treatment should be discontinued.

The investigator must also contact the IRT to register the subject's discontinuation from study treatment.

Patients may voluntarily withdraw from the study for any reason at any time. They may be considered withdrawn if they state an intention to withdraw, fail to return for visits, or become lost to follow-up for any other reason.

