 - Patients who did not meet the responder criteria at Week 16, 28 or 40 will start receiving secukinumab 300 mg every 4 weeks and will continue this dose up to Week 48.
- Patients on placebo (**Group 3**) regardless of their responder status will start receiving secukinumab 300 mg every 4 weeks from Week 16 up to Week 48.

Those patients whose tender and swollen joint counts both reduce by $\ge 20\%$ from baseline will be classified as 'responders' and those patients who do not meet the responder criteria will be classified as 'nonresponders'.

Patients, investigators/site staff, persons performing assessments, and Novartis study personnel will remain blinded to individual treatment assignment from the time of randomization until the final database lock.

Rescue medication will not be allowed during the day of the clinical visit and before

completion of Week 16 assessments. Although no subject will be restricted from receiving necessary rescue medications for lack of benefit or worsening of disease, patients will be discontinued from the study if rescued with prohibited biologics and should obtain end of study assessments at the earliest possible date, provided consent to do so has not been withdrawn.

No stratification at randomization will be performed.

The following figure describes the study design.

Figure 1.1: Study Design

Primary analysis time point

The primary analysis will be performed at Week 16.

Interim analyses

As planned, database lock will be performed at the end of Treatment Period 1 (Week 16), after all patients have completed the Week 16 visit. Data analyses will follow after first database lock.

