2.5.3 Handling of missing values/censoring/discontinuations

Patients who discontinued prematurely for any reason will be considered non-responders from the time they discontinued. Patients who do not have the required data to compute ACR20 response (i.e., tender and swollen joint counts and at least three of the five ACR components) at baseline and at the specific time point will be classified as non-responders.

In an additional analysis, missing data for ACR20 response variable will be handled by multiple imputation. Multiple imputation is a simulation-based approach where missing values are replaced by multiple Bayesian draws from the conditional distribution of missing data given the observed data and explanatory variables, creating multiple completed data sets. These completed data sets can then be analyzed using standard methods. Within this analysis, the ACR components will be imputed and response variables will be derived based on the imputed scores. In the multiple imputation analysis, the response status will be imputed based on the individual treatment arm information.

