EXCL22	Subjects with current severe progressive or uncontrolled disease which in the judgment of the clinical investigator renders the patient unsuitable for the trial.	1	Include in everything
EXCL23	Subject's inability or unwillingness to undergo repeated venipuncture (e.g., because of poor tolerability or lack of access to veins) should not be included in the study.	1	Include in everything
EXCL24	Subject with any medical or psychiatric condition which, in the Investigator's opinion, would preclude the participant from adhering to the protocol or completing the study per protocol should not be included in the study	1	Include in everything
EXCL25	Subject donation or subject with loss of 400 mL or more of blood within 8 weeks before	1	Include in everything

	dosing (randomization) should not be included in the study		
EXCL26	Subjects with the history or evidence of ongoing alcohol or drug abuse, within the last six months before randomization should not be included in the study	1	Include in everything
EXCL27	Subjects who have plans for administration of live vaccines during the study period or 6 weeks prior to randomization should not be included in the study	1	Include in everything
TRT01	Incorrect study medication administered by subject	4	Include in everything
TRT02	Any incorrect route of administration of study drug used at any time during the study, per protocol	4	Include in everything
TRT03	Two records with same "Date of dose" (i.e., Injection A and B)	4	Include in everything
TRT04	At Weeks 16, 28 and 40 patients on secukinumab 150 mg (Group 2) who are responders will continue to receive secukinumab 150 mg (1.0 mL) plus placebo (1.0 mL) every 4 weeks until next evaluation of responder status at weeks 28 or 40.	4	Include in everything
TRT05	Patients who did not meet the responder criteria at Week 16, 28 or 40 will start receiving secukinumab 300 mg s.c.every 4 weeks and will continue this dose up to Week 52.	4	Include in everything
TRT06	Missed or partial doses of study medication administered by subject	4	Include in everything
COMD01	Use of prohibited medication at any time during the study after randomization until Week 16	5	Include in everything
COMD02	Use of prohibited medication with potential impact on key efficacy and/or safety evaluations at any time during the study after Week 16	5	Include in everything
COMD03	subject received a live virus vaccination during the study	5	Include in everything

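### The primary ACR20 rule does not cover banned non-biologic joint rescue before Week 16 in a patient who stays in the study and has Week 16 data

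*Protocol*

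**What the plan says.** **Primary response rule.** Protocol 9.4.3, repeated in SAP 2.5.3, has two triggers for non-response. One is discontinuation: "Patients who discontinued prematurely for any reason will be considered non-responders from the time they discontinued". The other is lack of the data needed to compute ACR response.

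**Rescue.** Protocol 5.5.6 states: "Rescue medication must not be used before completion of Week 16 assessments". Protocol 5.5.7 bars intra-articular corticosteroids up to Week 16, and Table 5-1 prohibits conventional DMARDs other than methotrexate. Protocol 3.1 and SAP 1.1 also carry a patient safeguard, that "no subject will be restricted from receiving necessary rescue medications", and the same sentence gives the consequence for one class of drug: "patients will be discontinued from the study if rescued with prohibited biologics".

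**Routes to discontinuation.** Protocol 5.5.9 requires stopping treatment for:
- use of a biologic immunomodulator;
- incompatible severe or serious adverse events, "including adverse events that require treatment with an unacceptable co-medication";
- deviations that put the patient at significant risk.

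It adds that "the investigator should discontinue study treatment for a given subject if there is a lack of improvement or worsening of their symptoms".

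**Analysis.** SAP Table 5.5-1 lists deviation COMD01, "Use of prohibited medication at any time during the study after randomization until Week 16", and keeps such patients in every analysis set. Beyond the primary model there is a CMH test (SAP 2.5.4) and a multiple-imputation analysis: "In an additional analysis, missing data for ACR20 response variable will be handled by multiple imputation". SAP 2.3.1 tabulates deviations. SAP 2.4.2 summarizes rescue and lists concomitant medication.

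**The concern.** Most patients who need rescue before Week 16 should reach non-response through one of the discontinuation routes. One case is left: a patient receives a banned non-biologic that acts on joints, the investigator does not stop treatment, and Week 16 data exist. Neither trigger in 9.4.3 applies, so the observed ACR20 result counts.

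The same clinical event, inadequate control leading to rescue, is then scored in two ways depending on the drug chosen. A response produced by a steroid injection can be credited to the randomized arm. If that happens more often on placebo, the reported odds ratio understates the effect of the drug.

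**Working it through.** **1. Do the rules leave the case open?**

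| Event before Week 16 | Discontinuation required? | ACR20 status |
|---|---|---|
| Biologic rescue | Yes (3.1, 5.5.9) | Non-responder |
| Severe or serious AE needing an unacceptable drug | Yes (5.5.9) | Non-responder |
| Lack of improvement or worsening | Investigator judgment (5.5.9) | Non-responder if stopped |
| Banned steroid injection or conventional DMARD, not stopped, Week 16 data present | No, unless another 5.5.9 criterion applies | Observed value |

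The COMD01 entry settles analysis-set membership, not response status. Multiple imputation replaces missing values only, and the CMH test uses the same response variable.

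**2. The plan's sample size.** Inputs from protocol 9.7: 20% v 50%, ratio k = 2, two-sided 0.05, power 0.90, continuity-corrected chi-squared test.
- Pooled rate: (0.2 + 2×0.5)/3 = 0.4.
- Uncorrected placebo n = [1.96√(0.4×0.6×1.5) + 1.2816√(0.16 + 0.25/2)]²/0.3² = 38.4, so 39 (and 78).
- Corrected n = (38.4/4)[1 + √(1 + 2(k+1)/(38.4×k×0.3))]² = 43.3, so 44 (and 88). This matches the plan.
- Dropout: 44/0.9 = 49 and 88/0.9 = 98, rounded to 50 and 100.

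**3. Leverage fixed by the arm sizes.** One patient re-scored moves the placebo rate by 1/50 = 2 points or the 300 mg rate by 1/100 = 1 point.

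**4. Tipping point, with no rescue rate assumed.** z = [difference − ½(1/100 + 1/50)]/√[p̄(1−p̄)(1/100 + 1/50)].
- 50/100 v 10/50: (0.30 − 0.015)/√(0.24×0.03) = 3.36, p = 0.0008.
- 50/100 v 15/50: (0.20 − 0.015)/√(0.2456×0.03) = 2.16, p = 0.031.
- 50/100 v 16/50: (0.18 − 0.015)/√(0.2464×0.03) = 1.92, p = 0.055.

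So 16 − 10 = 6 placebo conversions, with none on 300 mg, would lose significance. Near the boundary one patient is enough: 10/50 on placebo needs 38/100 on 300 mg, and 11/50 needs 40/100.

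**5. Illustration on assumed rates.** The documents give no rescue rate. Let a share r of would-be non-responders be rescued and a share s of those meet ACR20. Then p0 = 0.2 + 0.8rs and p1 = 0.5 + 0.5rs. Under a composite rule, let a share q of would-be responders in each arm also trigger it, so p0 = 0.2(1−q) and p1 = 0.5(1−q). Power is by exact enumeration of the two binomials (100 and 50) with the test above, not the logistic model.

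| Scoring | Assumption | 300 mg v placebo | Difference (points) | Power |
|---|---|---|---|---|
| Plan | none | 50% v 20% | 30.0 | 0.942 |
| Observed | r=5%, s=20% | 50.5% v 20.8% | 29.7 | 0.934 |
| Observed | r=10%, s=40% | 52.0% v 23.2% | 28.8 | 0.910 |
| Observed | r=25%, s=40% | 55.0% v 28.0% | 27.0 | 0.855 |
| Composite | q=5% | 47.5% v 19.0% | 28.5 | 0.922 |
| Composite | q=10% | 45.0% v 18.0% | 27.0 | 0.899 |

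**6. Direction.** Here the assumed rescue shares are of the whole arm, half of the rescued patients respond, and the composite truth is 20% v 50%.
- Placebo 10%, 300 mg 3%: 51.5% v 25.0%, odds ratio 3.19.
- 10% in both arms: 55% v 25%, difference still 30 points, odds ratio 3.67.
- Placebo 2%, 300 mg 8%: 54% v 21%, odds ratio 4.42.

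Only the last pattern favours the drug.

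**The case against.** The strongest reply is that the handling can be inferred. Patients are analysed as randomized, SAP 2.1 uses all scheduled-visit assessments, and COMD01 foresees the event and keeps the patient in. Together these amount to a treatment-policy approach to non-biologic co-medication. On that view one rule keyed to discontinuation covers both drug classes without inconsistency. This is a defensible reading, but neither document states it as a choice, and it sits beside a failure rule for every patient who discontinues.

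The case is also narrow. The patient must break the ban, escape the instruction to stop for lack of improvement, have Week 16 data, and respond because of rescue. NSAIDs, low-strength opioids and acetaminophen must be withheld for at least a day before assessment visits (5.5.7), which limits carry-over from those drugs. All of this stands and is why the priority is low.

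Three stronger readings are tempting, and the documents do not support them:
- A reader might infer that the plan permits rescue before Week 16, because the safeguard sentence in 3.1 carries no time limit. The ban in 5.5.6 governs.
- A reader might infer that the exposure would go unseen. Deviation counts, a rescue summary and a medication listing are planned. What is not visible is a link to ACR20, and SAP 2.13 is absent from the available text, so even that statement is limited to what can be read.
- A reader might infer that a composite rule would raise power. With q=10% it gives 0.899, below the 0.910 for observed scoring at r=10%, s=40%.

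**Conclusion.** The gap holds as a low-priority point. Under 9.4.3 and SAP 2.5.3, prohibited non-biologic joint rescue before Week 16 does not by itself make a patient a non-responder, whereas biologic rescue does so through discontinuation.

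The likelier direction is dilution. At the planned rates placebo has 80% would-be non-responders against 50% on 300 mg, so more placebo patients are candidates for rescue. A reader might infer that the omission inflates the drug effect. That would need more rescue-driven response on 300 mg, and nothing in the documents suggests it.

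The size is unknown and possibly nil. In the scenarios of step 5, power falls below the planned 0.90 only when a quarter of would-be non-responders break the ban and 40% of them then respond. Every r, s, q and arm-specific rescue share is an assumption. The sample size is correct and unaffected. The case for change is consistent scoring of rescue, not power or type I error.

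**What to change.** Add to protocol 9.4.3 and SAP 2.5.3:

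> A patient who, after randomization and before completing the Week 16 assessments, receives rescue as defined in protocol 5.5.6 (given for no benefit or worsening of PsA, including a new or increased NSAID, analgesic, systemic corticosteroid or methotrexate given for that reason), or any intra-articular, intramuscular or intravenous corticosteroid, or any conventional DMARD other than methotrexate, is an ACR20 non-responder from first use through Week 16.

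- Cite the 5.5.6 definition explicitly, because SAP 2.4.2 words rescue differently. Tying NSAIDs and analgesics to the reason for use keeps a tablet for an unrelated headache from counting as failure.
- Identify these patients from the concomitant medication data while still blinded. Keep them in the Full Analysis Set, and report the observed-value analysis as a sensitivity analysis.
- If the Week 16 data are already unblinded, leave the primary rule alone and report the composite rule as a labelled sensitivity analysis. The SAP change log already carries entries made after the Week 16 lock, so this may be the applicable route.
- Leave the safeguard sentence in 3.1 and SAP 1.1 as it is. Limiting it to after Week 16 would remove a protection during the placebo period and blur the biologic discontinuation clause.

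**Cost:** one sentence in each document, one blinded medication review and one extra analysis. No new data or patients are needed. The downside is that a few patients who would have responded anyway count as failures. If that were 10% of would-be responders in each arm, the rates would be 45% v 18% and power about 0.90.

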9.4.4 Supportive analyses

The primary efficacy variable will also be analyzed at each time point for the Full Analysis Set using the Cochran-Mantel-Haenszel (CMH) test to compare each dose of secukinumab against placebo, adjusting for methotrexate usage at baseline (yes, no) (Stokes, Davis, and Koch, 2012). If the treatment comparison p-value is < 0.05 and the proportion of patients who are ACR20 responders is higher in a secukinumab treatment group compared to the placebo treatment group, statistical significance in favor of that dose of secukinumab is shown. Two 95% confidence intervals for the difference between each dose of secukinumab versus placebo in the proportion of patients who are ACR20 responders will be calculated using the normal approximation to the binomial distribution.

